3.0 Clinical Protocol

3.1 Study Design and Scope

This study is a prospective, non-randomized, multi-center, international post market study that will determine the prevalence and incidence of externalized conductors and other visual lead anomalies (as evidenced by imaging) and the risk of progression to electrical dysfunction in a large series of ICD/ CRT-D/CRT-P devices containing one or more of the following SJM leads: Riata leads, Riata ST silicone leads, Durata leads, QuickSite/QuickFlex CRT leads. A patient that has at least one market released lead implanted in time period indicated in Table 1 is eligible for enrollment in the study. Each lead group will be considered separately for independent analysis.

Table 1: Leads Eligible for Enrollment

Lead Group	Model Numbers	Lead Implant Date
Riata	1560, 1561, 1562, 1570, 1571, 1572, 1580, 1581, 1582, 1590, 1591, 1592	2002-2009
Riata ST Silicone	7000, 7001, 7002, 7010, 7011, 7040, 7041, 7042	2006-2009
QuickSite/QuickFlex	1056T, 1058T, 1156T, 1158T	2006-2010
Durata	7120, 7121, 7122, 7130, 7131, 7120Q, 7121Q, 7122Q, 7170Q, 7171Q, 7172Q	2008-2010

In order to determine the prevalence and incidence of externalized conductors, other visual lead anomalies as well as electrical dysfunction in the population of leads being evaluated, a minimum of 1500 leads listed above will be enrolled at up to 60 sites. This will comprise a minimum of 300 leads in the Riata lead group and a minimum of 200 leads in the Riata ST lead group to make a combined total of at least 500 Riata and Riata ST silicone leads. The study will also include at least 500 leads in the QuickSite/QuickFlex and Durata lead groups. All patients will be followed every six months for three years.

Adequate representation across the different ages of the leads is also needed to understand the lead population being studied. Therefore, the leads from each group of leads will be compromised of subgroups based on the age of lead (at enrollment) being studied. The required minimum enrollment for each subgroup per lead group is indicated in Table 2. Even if the minimum enrollments indicated in Table 2 are met, extra enrollments may be required to ensure a minimum of 500 leads in each lead group.

Expected Attrition in patients with high voltage leads

Withdrawals due to death

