Assuming an annual mortality of 7% in the ICD patient population, the mortality at 3 years is 20% $[1 - (1-0.07)^3]$ In the recent RHYTHM ICD/QuickSite 1056K left heart lead study, the annual mortality was 12.8%, which would result in a mortality of 33.7% $[1 - (1-0.128)^3]$ at 3 years. If the ICD:CRT-D device mix is 60%:40% then the expected overall mortality in this study at 3 years is 25.5% ($=0.6 \times 0.20 + 0.4 \times 0.337$).

Withdrawals due to reasons other than death

In an ongoing St. Jude Medical post-approval study (SJ4 PAS), the attrition rate due to reasons other than death at 22 months of follow-up is 9%. Thus, it is anticipated that the attrition rate at 3 years for reasons other than death will be 15%.

Assuming that deaths and withdrawals are independent events, the total attrition is expected to be approximately 37% ($= 1 - (1-0.255) \times (1-0.15)$) over 3 years.

Since the Riata/Riata ST leads are recalled, it is more likely that some physicians will explant them, even when electrical function is normal. For this reason, an additional 10% of the patients are expected to be prematurely withdrawn. This leads to a total attrition of approximately 43% ($= 1 - (1-0.255) \times (1-0.15) \times (1-0.10)$) over 3 years.

Expected Attrition in patients with left ventricular leads
Withdrawals due to deaths

In the RHYTHM ICD/QuickSite 1056K left heart lead study, the annual mortality was 12.8%, providing an estimated mortality rate of 33.7 % $[1 - (1-0.128)^3]$ at 3 years.

Withdrawals for reasons other than death

In the ongoing St. Jude Medical post-approval study, the attrition rate due to reasons other than death at 22 months of follow-up is 9%. Thus, it is anticipated that the attrition rate at 3 years for reasons other than death will be 15%.

Assuming that deaths and withdrawals are independent events, the total attrition is expected to be approximately 43.6% ($= 1-(1-0.337) \times (1-0.15)$) over 3 years.

Table 2: Enrollment in Lead Subgroups

Lead Group	Age of Lead at Enrollment (Years)	Min Enrollment	Expected Attrition at 3 years*	Target Enrollment
Riata Silicone	≥ 7	100	47%	195
	≥ 6 and < 7	100	45%	185
	< 6	100	43%	180
Riata ST	≥ 5.5	100	45%	185
	< 5.5	100	43%	180
QuickSite 1056T/1058 and QuickFlex 1156T/1158T	≥ 6	115	46%	225
	≥ 5 and < 6	115	46%	225
	< 5	170	44%	300
Durata	≥ 5	167	37%	275
	≥ 4 and < 5	167	37%	275
	< 4	167	37%	275

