3.2 Study Outcome Measures

3.2.1 Primary Outcome Measures

3.2.1.1 The prevalence of electrical dysfunction in the Riata, Riata ST, QuickSite/QuickFlex (1056T, 1058T, 1156T, 1158) and Durata leads.

Lead Population

All enrolled leads within the Riata, Riata ST, QuickSite/QuickFlex (1056T, 1058T, 1156T, 1158) and Durata lead groups.

Analysis:

The prevalence of electrical dysfunction will be calculated as the number of leads that have electrical dysfunction at the time of enrollment in each of the 4 lead groups divided by total number of leads in enrolled patients in each of the 4 lead groups. The one-sided 95% UCB for prevalence will be calculated using Clopper-Pearson exact method.

3.2.1.2 The prevalence of externalized conductors in the Riata, Riata ST, QuickSite/QuickFlex (1056T, 1058T, 1156T, 1158) and Durata leads.

Lead Population

All enrolled leads within the Riata, Riata ST, QuickSite/QuickFlex (1056T, 1058T, 1156T, 1158) and Durata lead groups.

Analysis:

The prevalence of externalized conductors will be calculated as the number of leads that have been shown to have externalized conductors by imaging at the time of enrollment in each of the 4 lead groups divided by total number of leads in enrolled patients in each of the 4 lead groups. The one-sided 95% UCB for prevalence will be calculated using Clopper-Pearson exact method.

3.2.1.3 The prevalence of other visual lead anomalies by each subcategory (fracture, kink, subclavian crush, other irregularities) in the Riata, Riata ST, QuickSite/QuickFlex (1056T, 1058T, 1156T, 1158) and Durata leads.

Lead Population

All enrolled leads within the Riata, Riata ST, QuickSite/QuickFlex (1056T, 1058T, 1156T, 1158) and Durata lead groups.

Analysis:

The prevalence of other visual lead anomalies (by each subcategory) will be calculated as the number of leads that have been shown to have other visual anomaly (by each subcategory) at the time of enrollment in each of the 4 lead groups divided by total number of leads in enrolled patients in each of the 4 lead groups. The one-sided 95% UCB for prevalence will be calculated using Clopper-Pearson exact method.

3.2.1.4 The annual hazard rate of lead electrical dysfunction (from enrollment) by lead subgroups in the Riata, Riata ST, QuickSite/QuickFlex (1056T, 1058T, 1156T, 1158) and Durata leads.

Lead Population

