All enrolled leads being followed in this study within the Riata, Riata ST, QuickSite/QuickFlex (1056T, 1058T, 1156T, 1158) and Durata lead groups.

Analysis:

The annual hazard rate will be assessed separately in each of the 4 lead groups along with the subgroups listed in Table 2.

For QuickSite/QuickFlex leads only, data from patients with an additional 1 year of follow-up will contribute to 2 separate lead subgroups (See Section 3.4.5).

3.2.1.5 The annual hazard rate of new cases of externalized conductors (from enrollment), by lead subgroups in the Riata, Riata ST, QuickSite/QuickFlex (1056T, 1058T, 1156T, 1158) and Durata leads.

Lead Population

All enrolled leads being followed in this study within the Riata, Riata ST, QuickSite/QuickFlex (1056T, 1058T, 1156T, 1158) and Durata lead groups.

Analysis:

The annual hazard rate will be assessed separately in each of the 4 lead groups along with the subgroups listed in Table 2.

For QuickSite/QuickFlex leads only, data from patients with an additional 1 year of follow-up will contribute to 2 separate lead subgroups (See Section 3.4.5).

3.2.1.6 The annual hazard rate of new cases of other visual lead anomalies by each subcategory (from enrollment), by lead subgroups in the Riata, Riata ST, QuickSite/QuickFlex (1056T, 1058T, 1156T, 1158) and Durata leads.**Lead Population**

All enrolled leads being followed in this study within the Riata, Riata ST, QuickSite/QuickFlex (1056T, 1058T, 1156T, 1158) and Durata lead groups.

Analysis:

The annual hazard rate will be assessed separately in each of the 4 lead groups along with the subgroups listed in Table 2.

For QuickSite/QuickFlex leads only, data from patients with an additional 1 year of follow-up will contribute to 2 separate lead subgroups (See Section 3.4.5).

3.2.1.7 Prevalence of “other insulation anomalies” in “returned leads” (as defined in section 2.0), by lead subgroups in the Riata, Riata ST, QuickSite/QuickFlex (1056T, 1058T, 1156T, 1158) and Durata leads.**Lead Population**

Any enrolled lead in the study that gets returned to St. Jude Medical for analysis.

Analysis:

The prevalence of “other insulation anomalies” will be calculated as the number of returned leads that have “other insulation anomalies” in each of the 4 lead groups divided by the total number of returned leads in enrolled patients in each of the 4 lead groups. The one-sided 95% UCB for prevalence will be calculated using Clopper-Pearson exact method.

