3.4.5 Extended Follow-up (Eligible QuickSite/QuickFlex patients only)

The purpose of extending follow-up for eligible patients with QuickSite/QuickFlex leads is to address challenges with fulfilling the minimum number of leads to enroll for the QuickSite/QuickFlex lead group/subgroups as shown in Table 2.

The extended follow-up will help address this issue since the data from patients with extended follow-up will contribute to 2 separate sub-group cohorts for the primary and secondary outcome measure analyses.

For example, a patient who was enrolled with a QuickSite/QuickFlex lead that was implanted for 5 years at the time of enrollment will contribute to the ≥ 5 to <6 year age of lead subgroup cohort (data from lead 5, 6, 7, and 8 years implanted). After this patient provides consent and completes the additional year of follow-up, this patient will also contribute to the ≥ 6 year age of lead subgroup cohort (data from lead 6, 7, 8, and 9 years implanted) as shown in Table 5 below.

Table 5: Extended Follow-Up Example

QS/QF Subgroup cohort Age of Lead @ Enrollment	Primary and Secondary Outcome Measure Data Analyses Timepoints				Extended Follow-up
	Enrollment /Baseline	12 Mo. Visit	24 Mo. Visit	36 Mo. Visit	
≥ 5 and <6 year	5 yr. lead data	6 yr. lead data	7 yr. lead data	8 yr. lead data	9 yr. lead data
≥ 6 year	6 yr. lead data	7 yr. lead data	8 yr. lead data	9 yr. lead data	

Patients eligible for extended follow-up are those already enrolled with QuickSite/QuickFlex leads that have not previously withdrawn and have a QuickSite/QuickFlex lead that will contribute to a second subgroup cohort with an additional year of follow-up.

In order to maintain an unbiased study design, all eligible patients will be approached to provide consent for extended follow-up. SJM will provide study sites with a list of all eligible patients upon approval of this protocol. After eligible patients have been approached to consent for extended follow-up, complete the Extended Follow-Up Consent CRF using the EDC system.

Eligible patients must provide consent for extended follow-up prior to completing the 42 and 48 month follow-up visits (See Section 14.0). Refer to Table 3 and Section 3.4.2 for the requirements for these additional follow-up visits.

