Appendix D: Revision History

Revision History				
Amendment Number	Version	Date	Rationale	Details
2	K	18Sept2015	
 • Change lead subgroup cohort defined by lead implant date to age of lead at enrollment (in years) and added Riata leads implanted in 2002 and 2003 to the eligible leads for enrollment in order to complete enrollments in a timely manner while adhering to the original 522 order study design (analyses of lead subgroups by age of lead). • Increased number of sites from 50 to 60 to increase enrollment rate • Added extended follow-up for eligible patients already enrolled with QuickSite/QuickFlex leads in order to address challenges with completing enrollments with this lead group/sub-groups. 	
Updates:
 
 • Table 1 and 2 • Enrollment Timeline • Sections 3.2.1, 3.3.1 • Sections 3.1, Appendix B. • Sections 3.2.1, 3.2.2, 3.4, 3.4.5, 14.0, Appendix C • Tables 3 and 5

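### Primary hazards grouped by lead age at enrollment do not show hazard at a given lead age; in the three one-year bands about 79–80% of lead-time lies above the band, so an attained-age hazard should be added

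*Combined protocol and SAP*

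**What the plan says.** Section 3.2.1.4 defines the outcome as "The annual hazard rate of lead electrical dysfunction (from enrollment) by lead subgroups"; 3.2.1.5 and 3.2.1.6 do the same for externalized conductors and other visual anomalies. All three give the same analysis: "The annual hazard rate will be assessed separately in each of the 4 lead groups along with the subgroups listed in Table 2". No hazard formula is given.

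Section 3.1 forms "subgroups based on the age of lead (at enrollment) being studied", and the Table 2 column is headed "Age of Lead at Enrollment (Years". On duration it says: "All patients will be followed every six months for three years". The reason offered for the bands is: "Adequate representation across the different ages of the leads is also needed to understand the lead population being studied". Appendix D says the change to age bands was made while "adhering to the original 522 order study design (analyses of lead subgroups by age of lead".

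Section 3.4.5 and Table 5 show how the bands fill. A QuickSite/QuickFlex lead enrolled at 5 years supplies the 5 to <6 band with "data from lead 5, 6, 7, and 8 years implanted". With a fourth year of follow-up, the same lead also supplies the ≥6 band with its data at 6, 7, 8 and 9 years. Nothing in 3.2.1.4–3.2.1.6 moves the time of any other lead to an older band as it ages.

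**The concern.** The Introduction presents these failures as abrasion, so dependence on time since implant is plausible, and Appendix D describes the design as analysis by age of lead. A band one year wide, fixed at entry and followed for three years, mostly describes older leads than its label suggests. If risk changes with lead age, a reader who takes the 5 to <6 result as the hazard of a five-year-old lead will misread it, and contrasts between neighbouring bands are blurred because both contain time at the same ages.

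The plan also applies two ageing rules. An extended QuickSite/QuickFlex lead that crosses a cut-point is re-entered in the older band. A Riata lead crossing 7, a Durata lead crossing 5, or a QuickSite/QuickFlex lead without the extra year is not.

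**Working it through.** **Reproducing the plan's attrition (section 3.1).** These are the only stated figures that feed the calculation.
- High-voltage leads: 1 − (1 − 0.255)(1 − 0.15) = 36.7%, stated as 37%.
- Riata/Riata ST: 1 − (1 − 0.255)(1 − 0.15)(1 − 0.10) = 43.0%, stated as 43%.
- Left ventricular leads: 1 − (1 − 0.337)(1 − 0.15) = 43.6%, as stated.

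All three reproduce. Table 2 then sets attrition by band: 45% for Riata 6 to <7, 46% for QuickSite/QuickFlex 5 to <6 and 37% for Durata 4 to <5.

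**Assumptions not in the documents.** Entry ages are uniform within a band, and leads exit at a constant rate λ that gives the Table 2 attrition D at three years.

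**Formulas for a one-year band.**
- λ = −ln(1 − D)/3
- Lead-years per enrolled lead: T = D/λ
- Lead-years inside the band, averaged over entry age: B = (1/λ)[1 − (1 − e^(−λ))/λ]
- Share above the band: 1 − B/T

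| Band | D | λ | T | B | Share above band |
|---|---|---|---|---|---|
| Durata 4 to <5 | 37% | 0.154 | 2.402 | 0.475 | 80.2% |
| Riata 6 to <7 | 45% | 0.199 | 2.258 | 0.468 | 79.3% |
| QuickSite/QuickFlex 5 to <6 | 46% | 0.205 | 2.240 | 0.467 | 79.1% |

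With no attrition the share is 1 − 0.5/3 = 83.3%.

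**At Table 2 target enrollment**, the lead-years above the band are:
- Durata: 275 × 2.402 ≈ 661, of which about 530 above and 131 inside.
- Riata: 185 × 2.258 ≈ 418, of which about 331 above and 87 inside.
- QuickSite/QuickFlex: 225 × 2.240 ≈ 504, of which about 399 above and 105 inside.

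**The other eight bands.** The four top bands (≥7, ≥5.5, ≥6, ≥5) have no upper limit, so the share is 0%. The four bottom bands have no stated lower limit, so the share depends on an assumed width:
- Durata <4: 62–80% (width 2 to 1 years)
- QuickSite/QuickFlex <5: 45–79% (3 to 1 years)
- Riata <6: 34–61% (4 to 2 years)
- Riata ST <5.5: 39–61% (3.5 to 2 years)

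**Overlap of a one-year band with the band above.** This is the integral of the smaller of the two normalised lead-time densities over attained age. At 37% and 46% attrition it is 63–64% if entry ages in the upper band span one year, about 50% if two, and about 39% if three. A wider span lowers it further.

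**Double use in the extension.** For the lead in Table 5, the first cohort covers ages 5 to 8 and the second covers 6 to 9. Ages 6 to 8, which are months 12–36, sit in both, so two of the three lead-years in each cohort are the same lead-years.

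**The case against.** The strongest reply is that the plan does not mislabel its quantity. The outcome is stated as running from enrollment, the Table 2 column says age at enrollment, and the objectives in section 2.0 ask for incidence after enrollment. The risk over the next three years, given the lead's present age, is a sensible thing to tell a physician. This stands. A reader might infer that the primary analysis is an error to be replaced; the documents do not support that.

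Four further points also stand, wholly or in part.
- **Reach.** A reader might carry the 80% over to every subgroup. Only three of the eleven bands are one year wide.
- **Overlap.** A reader might infer that neighbouring bands mostly share the same ages. The upper end, about 64%, needs a band above that is also one year wide. Table 2 has no such pair, because every middle band sits below an open-ended one.
- **Size of distortion.** It is tempting to say by how much a band's hazard exceeds the hazard at the labelled age. That needs a hazard shape, and the documents give none. Under a constant hazard there is no distortion.
- **Undefined rate.** The plan does not say whether the annual hazard is pooled over three years or given for each year since enrollment. If by year, about half of year 1 and all of years 2 and 3 still lie above a one-year band. The planned Kaplan-Meier curves from enrollment also let a reader approximate attained age, so it would be too strong to say the trial cannot speak to lead age at all.

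The 522 order is not among the documents and may itself prescribe these bands. That is a reason to keep them, but not a reason against a second table.

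On practicality, conductor externalization and other visual anomalies are looked for at yearly cinefluoroscopy with a ±60-day window, so their dates are known only to within about a year. Enrollment minimums are also set by enrollment age, so attained-age bands will have uneven precision. Both points are right and are met in the fix.

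**Conclusion.** The point holds as a gap in what the hazards can show, not as a contradiction or an invalid analysis. In Riata 6 to <7, QuickSite/QuickFlex 5 to <6 and Durata 4 to <5, about 79–80% of lead-time is at ages above the band, given uniform entry and Table 2 attrition. The figure is not sensitive to attrition (83% with none). It does not extend to the top bands, and in the bottom bands it is set by widths the documents do not give. Overlap with the band above is about 39–64% for upper-band entry ages spanning three years down to one.

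The mechanism needs none of these assumptions: Table 5 shows it directly. The same table shows the uneven treatment of ageing, with extended leads counted in two bands for months 12–36 and all other leads left in their enrollment band. Whether the reported hazards would mislead in practice depends on how strongly hazard changes with lead age, which is unknown at this stage. This is a worthwhile low-cost improvement that serves the by-age purpose named in Appendix D.

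**What to change.** Keep Table 2 as the enrollment quota and keep the age-at-enrollment hazards. Add to 3.2.1.4–3.2.1.6:

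1. A pre-specified annual hazard by attained lead age, with years since implant as the time scale, each lead entering at its age at enrollment (delayed entry), and lead-time split at the Table 2 cut-points. Each lead-year and event, including those of the extended QuickSite/QuickFlex year, then counts once, at its true age.
2. For externalized conductors and other visual anomalies, treatment of the event as interval-censored between the last clear and the first positive imaging, or a stated convention such as the midpoint.
3. Lead-years and a confidence bound for each attained-age band, so that thin bands are visible.

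**Cost.** Added analysis text and one extra table. Eligibility under Table 1 already requires the implant date, so no new patients, visits or data are needed. The price is less controlled precision: the Durata 4 to <5 attained-age band, for example, would keep about 131 of the 661 lead-years from its own enrollees, plus time from leads enrolled younger that pass through those ages.

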3.2.2 Secondary Outcome Measures

3.2.2.1 Time from enrollment to externalized conductors by lead subgroups

Lead Population

All the leads without externalized conductors at enrollment within the Riata, Riata ST silicone, QuickSite/QuickFlex (1056T, 1058T, 1156T, 1158) and Durata lead groups

Analysis:

Time to externalized conductors will be analyzed using the Kaplan-Meier method. Those patients who do not experience externalized conductors will be censored 3 years after enrollment in this trial. A separate Kaplan-Meier curve will be calculated for each of the lead subgroups outlined in Table 2.

For QuickSite/QuickFlex leads only, data from patients with an additional 1 year of follow-up will contribute to 2 separate lead subgroups (See Section 3.4.5).

3.2.2.2 Time from enrollment to other visual lead anomalies (evidenced by imaging) by lead subgroups and each subcategory

Lead Population

All the leads without other visual lead anomalies at enrollment (by each subcategory) within the Riata, Riata ST silicone, QuickSite/QuickFlex (1056T, 1058T, 1156T, 1158) and Durata lead groups

Analysis:

Time to other visual lead anomalies (by each subcategory) will be analyzed using the Kaplan-Meier method. Those patients who do not experience other visual lead anomalies (by each subcategory) will be censored 3 years after enrollment in this trial. A separate Kaplan-Meier curve will be calculated for each of the lead subgroups outlined in Table 2.

For QuickSite/QuickFlex leads only, data from patients with an additional 1 year of follow-up will contribute to 2 separate lead subgroups (See Section 3.4.5).

